2.5. CLINICAL STUDIES WITH COVID-19

FNC-Hope1 was a randomized, open-label, controlled clinical trial to evaluate the safety and efficacy of AZVUDINE tablets in the treatment of COVID-19, conducted at *People's Hospital of Guangshan County*, China.

Twenty individuals with COVID-19 with mild to moderate symptoms were randomly and equally assigned to 2 groups, experimental and control. Subjects who received conventional treatment with FNC + (no antiviral drugs) after diagnosis **reduced** the time to become nucleic acid negative for the first time by -7.3 days, compared to those who received conventional treatment alone (9.8). Subjects who received conventional treatment + FNC (no antiviral drugs) reduced the time to nucleic acid

negative for the first time by -6.8 days compared to those who received conventional treatment alone (11,30).

[figure not shown]

Figure 3: Kaplan-Meier curves of two consecutive negative tests for SARS-CoV-2 (a) first and b) second) in FNC and control group. Data are percent (%). Differences between groups were using the Log-rank test (Mantel-Cox)

On the fourth day after treatment, the rate of the first negative nucleic acid conversion reached 100% in patients in the FNC group and 30% in patients in the control group. Kaplan-Meier curves indicate the significant difference (p = 0.0013). On day 6, the negative conversion rate of the second nucleic acid reached 100% in patients of the FNC group and 40% in patients of the control group. Kaplan-Meier curves indicate the significant difference (p = 0.0011).

Regarding the safety analysis, there was no adverse event in the experimental group and three adverse events in the control group with an incidence of 30% (3/10) during the study period. All adverse events were grade 2 and were followed up until they disappeared. There were no serious adverse events, serious adverse reactions, major adverse events, or death events during the study period. The demographics and baseline characteristics of the subjects were similar and the proportions between the 2 groups were relatively balanced and comparable.

In 3 other hospitals in China, during the periods February 14 to March 10, March 1 to March 22, and March 7 to March 30, 32 volunteers with mild to severe symptoms were treated with different antiviral therapeutic approaches, including Arbidol,

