11. STATISTICAL ANALYSIS

11.1. SAMPLE SIZE ESTIMATION

This study is a randomized, parallel, double-blind, PLACEBO-controlled clinical trial, with the primary endpoint being the "Proportion of participants with improvement in clinical status [Period: until D15, approximately 14 days]".

This is a randomized, parallel, double-blind, PLACEBO-controlled clinical trial, which after initial study data, the sample size calculation was revised by updating parameters of frequency of clinical improvement and dropout rate. The revised sample size is 180 participants randomly and equally divided into the two arms of the study (90 practitioners in each group).

- Proportion of participants (%) with improvement of clinical status [Period: until
 D15, approximately 14 days].
- Clinical improvement time (median, in days) taking into account the following **PARAMETERS:**

0	Level of Significance	α = 5%
0	Statistical test power	Not less than 80%;
0	Distribution into groups	1:1 ratio
0	Frequency of clinical improvement	p1 = 66.7% in the test
		group;
		p2 = 28.1% in the control
		group
0	Superior efficacy study in terms of	15% established in previous
	frequency of clinical improvement	studies;
0	Median time to clinical	5 days in the test group;
	improvement	7 days in the control group.
0	Minimum detectable HR risk rate	0,7
	over time for clinical improvement	

We use the results of the open-label, randomized, controlled trial report on the efficacy of AZVUDINE 1 mg tablets in the treatment of patients with COVID-19 (HOPE-1) ¹⁸, as reported below:

 The study included male/female patients 18 years and older with a mild course of COVID-19 who received treatment for COVID-19 ("treated") prior to enrollment in the study and, patients who did not receive treatment ("newly diagnosed"). All patients received AZVUDINE at a dose of 5 mg per day for 7 days;

- Analysis of this clinical trial shows that at the start of treatment, 100% of patients tested positive for SARS-CoV-2 RNA, 80% of patients had abnormalities on lung CT, and, 50% of patients had respiratory symptoms and signs.
- According to the WHO COVID-19 Ordinal Scale of Clinical Improvement, 50% of the patients were in category 1 and 50% were in category 2.

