The number of participants was calculated using R 4.0 software, as detailed below: Trial Size: Two Sample Proportion. NIS (alpha = 0.05, beta = 0.2, p1 = 0.667, p2 = 0.281, k = 1, delta = 0.386, margin = 0.205) = 80.043° 81 por Grupo.

Number of participants	Sample Size	Drop-out (10%)
162 being:	180	18
81 Placebo group	90 Placebo group	
81 Azvudine group	90 Azvudine group	

"The required sample size for the IGZ-1 protocol is 180 participants, with 90 participants in each group, considering the 10% chance of drop-outs (participants who leave the study for some reason other than its termination)."

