11.3. METHOD OF STATISTICAL ANALYSIS

All statistical tests will be two-sided tests.

- If the p-value is ≤0.05, it is considered that there is statistical significance in the test (unless otherwise specified).
- The quantitative indices describe the mean value, standard deviation, median, minimum value, maximum value, lower quartile (Q1), upper quartile (Q3) to be calculated, and the rank indices describe the frequency and percentage of cases.
- Comparison of the two groups under general conditions will be analyzed with appropriate methods according to the types of indicators. Student's ttest or Mann-Whitney test will be used to compare the groups for quantitative data. Chi-square test or Fisher's exact test will be used for categorical data.
- The selected cases should be grouped and at the end of the study determine the three analysis data sets (FAS, PPS, SS).
- For the analysis of demographic information and baseline eigenvalues, the mean value, standard deviation, quartiles, minimum value and maximum value should be calculated for numeric variables. For categorical data, frequency and percentage will be calculated.
- For analysis of medication and drug combination adherence one should calculate the percentage of individuals whose medication adherence is at

least 80-100%. An analysis of the classification of the combination of drugs should also be done.

• For analysis of the primary effectiveness indicator:

Primary Goal

To evaluate the **efficacy and safety of** AZVUDINE (FNC) versus placebo in patients infected with moderate to severe stage SARS-COV-2;

Analysis method:

For the efficacy analysis a logistic regression model will be used with the dependent variable "The proportion of participants with clinical improvement [Period: until D15, approximately 14 days]" and independent variables allocation group, AZVUDINE (FNC) or PLACEBO. For the Safety analysis a logistic regression model will be used with the dependent variable "occurrence of serious adverse events" and independent variables allocation group, AZVUDINE (FNC) or PLACEBO. As a support analysis, with exploratory character, both for efficacy and safety, covariate models will be built as well as other variables that present, in the univariate analysis, statistical significance.

Secondary objective

To evaluate the **clinical outcome** between the AZVUDINE (FNC) group versus placebo in patients infected with moderate to severe stage SARS-COV-2;

Analysis method:

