Univariate analysis of the clinical outcome variables and with the group variable.

- For the secondary efficacy indicator analysis, the coronavirus viral load changes compared to baseline should be calculated for the experimental and control groups separately, as well as the value of the difference between the viral load changes compared to baseline for both groups. The ANCOVA model will be used to estimate the impact of treatment on viral load changes adjusting for other study variables such as disease severity, age, weight, and comorbidities, etc.
 - For analysis of the secondary efficacy indicator one should stratify according to the severity of the disease (severe, severe), following the following statistical methods:

PRIMARY ENDPOINT			ANALYSIS METHOD
•	Propo	rtion of participants with clinical status	Teste t de
	impro	vement [Period: until D15,	Student/Teste de
	appro	ximately 14 days].	Mann-Whitney
	0	The criterion for a participant to have	
		an improvement in clinical status is a	
		decrease on the WHO Clinical	
		Improvement Ordinal Scale in at least	
		one category compared to screening	
		(WHO, Jun/2020).	

SEC	CONDARY OUTCOMES	
•	Proportion of participants with a clinical	Pearson's Chi-
	outcome of cure during the study; [Period:	square test
	until D15, D21, and D28, approximately 14-	
	30 days].	

;	inic	al Trial Design	
		o The clinical endpoint of cure is	Student's t-test /
		defined in this protocol as the	Mann-Whitney
		absence of viral RNA in	test
		collected samples and clinical	
		conditions for	
		hospital discharge.	
	•	Time to normalization of body temperature	Student's t-test /
		(below 37.6c, axillary); [Period: until D15,	Mann-Whitney
		D21 and D28, approximately 14-30 days].	test
		Time to improvement of diarrhea,	Student's t-test /
		myalgia, fatigue, malaise, cough and	Mann-Whitney
		headache; [Period: until D15, D21 and	test
		D28, approximately 14-30 days].	
		Changes in liver and kidney function	Student's t-test /
		baselines, and inflammatory and	Mann-Whitney
		immunological markers: [Period: until	test
		D15, D21 and D28, approximately 14-30	
		days]	
		 Lab tests performed on days D1, 	
		D3, D5, D7, D9, D13, D15, D21,	
		D28, and D60.	
		Evaluation of the time to negative	Student's t-test /
		conversion of SARS-CoV-2 viral load by	Mann-Whitney
		RT-PCR between AZVUDINE (FNC) group	test
		and placebo- control group; [Period: until	
		D15, D21 and D28, approximately 14-30	
		days].	

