- Evaluation of the number of cycles for the detection of SARS-CoV-2 viral load byRT-PCR and application of the standard curve for viral load calculation; [Period: until D15, D21 and D28, approximately 14-30 days].
- Student's t-test /
 Mann-Whitney
 test
- Analysis of the relationship between the calculated viral load and the clinical outcome of participants in the AZVUDINE (FNC) group versus the placebo control group; [Period: until D15, D21 and D28,

Generalized linearregression model

- approximately 14-30 days].
- Time and proportion of lung imaging improvement during treatment (Pattern of ground-glass opacities, mosaic paving, alveolar consolidation, reticular pattern/septal thickening, opacity with inverted halo, pleural/pericardial effusion, fibrosis and/or lymphadenomegaly); [Period: until D15, D21 and D28, approximately 14-30 days].

Student's t-test /
Mann-Whitney test
/ Pearson's chisquare test

 Time of improvement and proportion of respiratory symptoms and signs during treatment (Lung rales, cough, sputum, sore throat); [Period: until D15, D21, and D28, approximately 14-30 days].

Student's t-test /
Mann-Whitney test
/ Pearson's chisquare test

·IIIIIC	ai Illai Desigli	
•	Time to normalization of _{O2} saturation (above 95%); [Period: until D15, D21 and D28, approximately 14-30 days].	Student's t-test / Mann-Whitney test
•	Time to normalization of respiratory rate to levels ≤ 24rpm, in room air; [Period: until D15, D21 and D28, approximately 14-30 days]	Student's t-test / Mann-Whitney test
•	Frequency of supplemental oxygenation or non-invasive ventilation; [Period: until D15, D21 and D28, approximately 14-30 days].	Student's t-test / Mann-Whitney test / Pearson's chi- square test
•	Frequency of invasive mechanical ventilation or extracorporeal membrane oxygenation (ECMO); [Period: until D15, D21 and D28, approximately 14-30 days].	Student's t-test / Mann-Whitney test
•	Proportion of moderate cases that progressed to severe cases requiring intensive care unit (ICU) care; [Period: until D15, D21, and D28, approximately 14-30 days].	Pearson's Chi- square test
•	Length of hospital stay; [Period: until D15, D21 and D28, approximately 14-30 days].	Student's t-test / Mann-Whitney test

Jinicai Triai Design	
 Occurrence of drug interactions; [Period: until D15, D21 and D28, approximately 14- 30 days]. 	Pearson's Chi- square test

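### The method table gives time-to-event secondary endpoints only a t-test or Mann-Whitney test with no rule for patients without the event, and it contradicts the text on the primary test

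*Protocol*

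**What the plan says.** Section 11.3 opens with a general rule: "Student's ttest or Mann-Whitney test will be used to compare the groups for quantitative data". The next sentence assigns chi-square or Fisher's exact test to categorical data, and the section also states: "All statistical tests will be two-sided tests".

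The method table in the same section then names a test for each endpoint. Rows such as "Time to normalization of body temperature", symptom improvement, PCR negative conversion, oxygen saturation, respiratory rate and "Length of hospital stay; [Period: until D15, D21 and D28, approximately 14-30 days" carry Student's t / Mann-Whitney and nothing else. The imaging and respiratory-sign rows combine a time with a proportion. They list the same two tests, with Pearson's chi-square added. Each of these endpoints is followed to D15, D21 and D28.

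On the primary proportion, the text of section 11.3 specifies a logistic regression on allocation group, while the primary row of the table shows Student's t / Mann-Whitney. The row "Frequency of invasive mechanical ventilation or extracorporeal membrane oxygenation (ECMO)" also shows only Student's t / Mann-Whitney.

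Elsewhere the protocol treats recovery times as survival data. The planning parameters in section 11.1 list median times to improvement of 5 and 7 days and a hazard ratio of 0.7. Section 2.5 reports the pilot trial's time to PCR negativity as "Kaplan-Meier curves indicate the significant difference (p = 0.0013)", and its Figure 3 caption names the log-rank test.

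**The concern.** A t-test or rank test needs one number per patient. A patient who has not recovered by the cut-off has no recovery time, and a patient who dies never will. Death is among the events that end participation (sections 1.1 and 9.3). The protocol does not say what value such patients receive.

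Under the plain complete-case reading they fall out. The test then compares speed of recovery among those who recovered, a group selected after randomisation and in a way that may depend on treatment. If one arm has more unresolved patients, its slowest patients are the ones removed, so the estimated difference shrinks and power is lost. Length of stay has a further problem: if stay is counted to the end of the admission whatever the reason, an early death scores as a short, apparently favourable stay.

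For the primary endpoint the issue is different. One section names two analyses for the same proportion, so the deciding p-value and effect measure are not fixed.

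**Working it through.** **Inputs**
- From section 11.1: "Not less than 80" percent power, alpha 5%, and "p1 = 0.667, p2 = 0.281, k = 1, delta = 0.386, margin = 0.205", giving 81 per group before dropout; medians of 5 and 7 days; the pilot trial's patient table.
- From section 11.3: two-sided tests.
- Assumed, not in the protocol: exponential times, and medians for the secondary endpoints equal to those listed for clinical improvement.

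**1. The plan's own figure.** n = (z_alpha + z_beta)² × [p1(1−p1) + p2(1−p2)] / (delta − margin)² = (1.645 + 0.842)² × (0.2221 + 0.2020) / 0.181² = 80.04, so 81 per group; 81/0.9 = 90 with dropout. This reproduces at one-sided alpha 0.05 (102 per group at one-sided 0.025), which is a separate matter. The 81 per group is used here only to set the scale of the illustration.

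**2. The mechanism in the protocol's own patient table (section 11.1).**
- Test-arm times: 3, 6, 4, 5, 1, 5, 4, 5, 5, 6; mean 44/10 = 4.4 days.
- Control times: 7, 4, 8, 5, 8, 6, 14, 7, 4, 14; mean 77/10 = 7.7 days. Difference 3.3 days.
- Cut at day 7, four controls (8, 8, 14, 14) and no test patient lack the event. The remaining control mean is 33/6 = 5.5 days, and the difference falls to 1.1.
- On patients with an event: t-test p = 0.17, Mann-Whitney p = 0.24. Log-rank on all 20, censored at day 7: p = 0.005.

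The day-7 cut and the 20 patients are only an example of the selection.

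**3. Expected size under the exponential assumption.** Rate = ln 2 / median. Unresolved fraction at cut-off c: S = exp(−rate × c). Mean among those resolved: 1/rate − c × S/(1 − S).

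| Cut-off | Unresolved, 5-day v 7-day median | Mean among resolved | Difference |
|---|---|---|---|
| Day 14 | 14.4% v 25.0% | 4.87 v 5.43 | 0.57 days |
| Day 28 | 2.1% v 6.3% | 6.62 v 8.23 | 1.6 days |

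The unconditional exponential means are 7.21 and 10.10 days, a difference of 2.9 days. The medians themselves differ by 2.

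**4. Simulated power (81 per arm, two-sided 5%, no deaths; repeat runs agree within about two percentage points).**

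| Cut-off | Non-events dropped: t / Mann-Whitney | Non-events kept at cut-off: t / Mann-Whitney | Log-rank |
|---|---|---|---|
| Day 14 | 14% / 13% | 46% / 43% | 49% |
| Day 28 | 34% / 30% | 54% / 46% | 55% |

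With identical arms, the tests on patients with an event reject in 4.6% to 5.3% of runs, so the false-positive rate is not inflated there.

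**5. Binary endpoints.** With 60 v 47 responders of 90 per arm: t-test p = 0.0488, Mann-Whitney p = 0.0491, Pearson chi-square p = 0.0484. Fisher's exact test is more conservative, at 0.068.

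**The case against.** The strongest reply is that the protocol never says patients without the event are dropped. That stands. Mann-Whitney is a sound test if non-events and deaths take the worst rank at a common cut-off, and step 4 shows that keeping them recovers most of the power. The large loss comes from the assumed dropping, not from the names of the tests. What remains is that neither a survival method nor any such rule is stated.

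The day-14 figures are also the least favourable choice; at day 28 few patients are unresolved and the loss is smaller. The medians belong to clinical improvement, which is not one of these secondary endpoints, and the protocol gives no distribution for the others. The power figures are therefore an illustration, not a forecast for this trial.

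A reader might infer that the comparison could reverse direction. The documents do not show this. It appears only in a constructed scenario (85% v 55% able to recover, the extra recoveries coming late), where the t-test on recovered patients is significant the wrong way in 29% of runs.

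A reader might also infer that binary endpoints in general get the wrong test. They do not: the general rule is chi-square or Fisher, and cure, ICU progression, drug interactions, supplemental oxygen and adverse events all list chi-square. The mortality cell is not legible enough to count.

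Finally, event times are not all exactly known. During treatment PCR is every 48 hours and CT every 4 days. The D21 visit is only for patients still in hospital, so someone discharged by D15 has no scheduled assessment until D28. Any survival analysis must allow for that.

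**Conclusion.** The point holds in this form. The protocol fixes a t-test or Mann-Whitney test for endpoints that are right-censored by design and subject to death, and it gives no rule for patients without the event. That leaves open a complete-case analysis conditional on recovery and a length-of-stay comparison that can credit early death. If non-events are dropped, the illustrative power loss is from 49% to about 14% at day 14 and from 55% to about 34% at day 28; if they are kept at the cut-off it is a few points at day 14. These figures rest on exponential times, borrowed medians, 81 per arm and no deaths.

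The primary endpoint has two conflicting analyses within section 11.3, and invasive ventilation/ECMO departs from the protocol's own categorical rule. The t-test, Mann-Whitney and chi-square p-values nearly coincide on binary data, so this is a contradiction to remove. It does not support a reading that the primary conclusion is invalid.

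This should be fixed, but it ranks below a fault in the primary analysis because the time endpoints are all secondary.

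**What to change.** In the section 11.3 table:

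- **Time endpoints.** Replace Student's t / Mann-Whitney with Kaplan-Meier curves, a log-rank test and a Cox hazard ratio, censored at one stated common cut-off (for example D28). Keep patients who die at risk as non-events to that cut-off.
- **Length of stay.** Analyse as time to live discharge, with the same cut-off and death rule.
- **PCR and CT times.** State that these are observed only at scheduled assessments, and define the event time, for example as the first scheduled assessment showing the event. Acknowledge the gap between discharge and D28.
- **Primary row.** Delete Student's t / Mann-Whitney so that logistic regression is the sole primary test.
- **Invasive ventilation/ECMO row.** Use chi-square, or Fisher's exact test under a stated sparse-table criterion, since the two can fall on different sides of 5%.

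The cost is wording and a little more analysis work. No new visits are needed: symptoms and vital signs are recorded daily in treatment, and PCR and CT follow the existing schedule. Section 5.4.4 places unblinding after the final statistical plan, so the change can be made before anyone sees results by arm.

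### Section 11.3 names two different methods for the yes/no primary endpoint; the t/Mann-Whitney entry should go, and the screening WHO score should be a pre-specified covariate in the logistic model

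*Protocol*

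**What the plan says.** Protocol Section 7.1.1 defines the primary endpoint as the proportion of participants whose WHO ordinal score falls by at least one category from screening, up to D15. Each participant therefore scores yes or no.

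Section 11.3 gives two analyses for it:

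- **Text, under the primary goal:** for efficacy, "a logistic regression model will be used with the dependent variable" clinical improvement until D15, and "independent variables allocation group, AZVUDINE (FNC) or PLACEBO". No other term is in the main model.
- **Methods table, row headed as the primary endpoint:** a cell left in Portuguese ("Student/Teste de" Mann-Whitney), that is, Student's t-test or Mann-Whitney.

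The general rules at the start of Section 11.3 assign t and Mann-Whitney to quantitative data and add: "Chi-square test or Fisher's exact test will be used for categorical data".

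Three further statements in Section 11.3 bear on the point:

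- Adjustment is exploratory support only: "covariate models will be built as well as other variables that present, in the univariate analysis, statistical significance".
- The secondary efficacy analysis is to "stratify according to the severity of the disease (severe, severe"), which names one stage twice.
- In the table, the row "Frequency of invasive mechanical ventilation" or ECMO lists only t/Mann-Whitney. The row just above it, on supplemental oxygen or non-invasive ventilation, also lists chi-square.

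**The concern.** A phase III trial needs one stated confirmatory test. Here one section states two, and the second breaks the section's own rule for categorical data. This is not a detail left to a statistical analysis plan, because the protocol itself fixes both methods.

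The practical question is what the t/Mann-Whitney row is applied to. On the 0/1 outcome it tests the same difference in responder rates as the logistic model. These are tests for quantitative data, however, so the row can also be read as a comparison of WHO scores or score changes. That would be a different hypothesis with a different effect measure.

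A lesser point is that the endpoint is measured from the screening score, yet that score is not in the main model. The only route to adjustment is exploratory, and there the added variables are chosen by their univariate p-values in the trial data.

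**Working it through.** **1. Group size for the illustrations.** Section 11.1 gives p1 = 0.667, p2 = 0.281, alpha = 0.05, beta = 0.2, delta = 0.386 and margin = 0.205.

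n = (z_alpha + z_beta)² × [p1(1−p1) + p2(1−p2)] / (delta − margin)²

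= (1.645 + 0.842)² × (0.2221 + 0.2020) / 0.181² = 6.183 × 0.42415 / 0.03276 = 80.04, rounded up to 81 per group.

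The protocol's figure is reproduced, with a one-sided z_alpha. That one-sidedness is a separate matter; 81 per arm is used here only as a realistic analysed size.

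**2. Both methods on the 0/1 outcome, 81 per arm, two-sided p-values.**

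| Improved, arm 1 vs arm 2 | Logistic (Wald) | t-test | Mann-Whitney | Chi-square | Fisher |
|---|---|---|---|---|---|
| 45 vs 32 | 0.0417 | 0.0411 | 0.0417 | 0.0408 | 0.0587 |
| 46 vs 34 | 0.0603 | 0.0599 | 0.0604 | 0.0593 | 0.0836 |

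The first three columns agree to within 0.001. Enumerating all outcomes at 81 per arm, the chance that logistic, t and Mann-Whitney fall on different sides of 0.05 is below 0.4% at true rates of 66.7/28.1% and at 60/60%.

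**3. Effect measures for 45 vs 32.** The t-test's mean difference is 45/81 − 32/81 = 13/81 = 0.160, which is the risk difference. The logistic model gives an odds ratio of (45 × 49)/(36 × 32) = 1.91. Mann-Whitney gives a rank shift. The sample size in Section 11.1 was set on a difference in proportions.

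**4. If the row means the score.** A test of mean or ranked WHO score, or of its change, counts how many categories a participant moves. A test of the responder rate counts only whether the participant moved down at all. The two need not agree, and Section 11.3 does not say which is intended.

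**5. What adjusting for the screening score is worth.** This was simulated with 81 per arm, two-sided 0.05 and 2,000 runs. Assumptions that are not in the protocol: scores 4/5/6 in 30/50/20% of participants, treatment log odds ratio 0.9, and a linear log-odds slope per category as shown.

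| Slope per category | Power, unadjusted | Power, adjusted | Type I error, unadjusted / adjusted |
|---|---|---|---|
| 0 | 81% | 81% | 4.6% / 4.8% |
| 0.7 | 76% | 78% | 4.9% / 5.0% |
| 1.4 | 66% | 73% | 4.3% / 4.2% |

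Type I error is 4% to 5% with or without the score. The gain in power runs from 0 to about 7 points.

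**The case against.** **Precedence and timing.** The logistic model stands under the primary goal, while the table follows an introduction about secondary indicators, so the text can be said to take precedence. Section 5.4.4 also allows unblinding only after the final statistical plan and database lock. Both points are fair. A reader might infer that two methods leave a free choice after unblinding; Section 5.4.4 does not support that. Even so, the row carries the primary-endpoint heading, and nothing says that the text overrides it.

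**Small numerical stakes.** This stands for the 0/1 outcome, as step 2 shows. It does not cover the reading in step 4.

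**Effect measure.** A reader might infer that a t-test gives nothing usable for a responder rate. Step 3 shows otherwise.

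**Baseline score.** An unadjusted logistic model is valid in a randomised trial. A reader might infer bias, or a large loss of precision; the protocol supports neither. It gives no improvement rates by starting score, and Table 4 does not settle the ordering: improving from 4 means leaving inpatient status, whereas 5 to 4 means only coming off oxygen.

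**HOPE-1.** Category 1 at screening was 8/10 in the test group and 2/10 in the control group (Section 11.1). A reader might take this as the imbalance to expect here. It comes from a 20-patient trial at scores 1 and 2. With 90 per arm, the 95% chance range for a 50% trait is about ±1.96 × √(2 × 0.25/90) = ±15 points, not 60.

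**Univariate selection.** It governs added variables in models labelled exploratory, so it cannot displace the primary result. It remains a poor basis for adjustment.

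**Ventilation row.** Frequency could mean a count or a duration, so the criticism applies only if the row is analysed as yes/no.

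**Conclusion.** The contradiction is real and should be corrected: one primary endpoint, two methods, and the second against the protocol's own rule for categorical data. Its numerical effect is negligible if both are run on the 0/1 outcome. It is undetermined if the table means the ordinal score or its change, because the tested quantity then differs.

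Leaving out the screening score is a missed gain in precision and not an error. The 0 to 7 power points rest wholly on the assumed score distribution, treatment effect and slopes in step 5. Nothing in the protocol makes age, or any other covariate beyond the screening score, a requirement.

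The repeated stage in the stratifier is probably a wording slip. As written it separates nothing, while Section 5.2.3 enrols both moderate and severe stages.

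**What to change.** In Section 11.3, before unblinding:

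1. Delete the t/Mann-Whitney entry from the primary endpoint row and state that logistic regression is the single primary analysis.
2. Add the screening WHO score as a pre-specified covariate, and state whether it enters as categories or linearly.
3. Report a standardised risk difference with a two-sided 95% CI, which matches the scale used in Section 11.1. Give the unadjusted model as a sensitivity analysis.
4. Remove univariate significance as the way to choose adjustment variables.
5. Where invasive ventilation or ECMO is analysed as yes/no, use chi-square or Fisher.
6. Correct the severity stratifier to match the enrolled moderate and severe stages.

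The cost is a wording change. The screening score is already needed to derive the endpoint, so no new data are collected. The one constraint is that the covariate and its form must be fixed before treatment codes are known.
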